Project title	A Danish Audit of Small Bowel Obstruction	
Participating Centres	Bispebjerg Hospital; Herlev Hospital; Hillerod Hospital; Hvidovre Hospital; Slagelse Hospital; Zealand University Hospital, Køge;	
Principal Investigator	[name] Abdominal Center K, Bispebjerg Hospital [contact]	
Local Investigators	Bispebjerg Hospital	[name] [contact]
	Herlev Hospital	[name] [contact]
	Hillerod Hospital	[name] [contact]
	Hvidovre Hospital	[name] [contact]
	Slagelse Hospital	[name] [contact]
	Zealand University Hospital, Køge	[name] [contact]

1. Background

Small bowel obstruction (SBO) is a common and potentially life-threatening acute surgical condition. A minority of patients present with a clear indication for urgent surgical intervention, either on the basis of clinical or radiological assessment (clinical signs of peritonitis/sepsis; suspicion of bowel ischaemia; closed loop obstructions; irreducible herniae etc.). However, the optimal management of the remaining patients, the majority of whom present with SBO caused by abdominal adhesions, remains a topic of international debate.

In the United Kingdom, the majority of patients with adhesional SBO are managed non-operatively unless a clear indication for acute surgery is found. This approach is based on both the rationale that the acute presentation may resolve with non-operative management and that surgical intervention may lead to the development of further adhesions, leading to further episodes of SBO in the future [1]. The management of adhesional SBO in Denmark is more surgically aggressive, where the majority of patients tend to undergo an acute or urgent operation unless there is a clear contraindication to surgery. The rationale for this approach is that the patient has been admitted with clinically significant adhesions, which will continue to cause intermittent obstruction unless divided. Although there is some evidence to support a more aggressive approach, with a recent retrospective study from Canada demonstrating fewer future episodes of SBO in patients undergoing operative management, the benefit of the acute surgical intervention must be balanced with the risks of peri-operative morbidity [2].

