In 2017, a snapshot audit of the outcomes of patients admitted with SBO in the UK was performed, including over 2,400 patients (<https://www.acpgbi.org.uk/content/uploads/2017/12/NASBO-REPORT-2017.pdf>) [3]. This audit not only identified variations in the management of patients with SBO but also identified several key recommendations to improve the outcomes of this patient group including earlier use of CT scanning, a more standardised approach to non-operative management, a greater focus on nutritional status and optimisation of peri- and post-operative care.

Standardised acute care bundles are now commonplace in Denmark. With a focus on early identification of high-risk surgical patients, these pathways facilitate early radiological diagnoses, pre/peri-operative patient optimisation and early, appropriate surgical intervention. Although one of the key patient groups identified by these pathways, the outcomes of patients admitted with SBO are not routinely audited, which limits further optimisation of patient care.

This quality assessment study aims to provide robust data on the outcomes of patients admitted with SBO in Region Øst in order to identify areas in need of improvement and further research.

2. Objectives

To perform a prospective quality assessment study of the outcomes of management of patients admitted with SBO in Region Øst.

Primary objective

- 30-day morbidity and mortality rates of patients admitted with SBO

Secondary objectives

- 90-day mortality rates of patients admitted with SBO
- To identify the most common causes of SBO in this patient cohort
- To investigate potential variability in the diagnosis and peri-operative management of these patients
- To determine what proportion of patients undergo non-operative vs operative management of SBO
- To determine the success rate of non-operative management in patients with SBO and identify predictors of success/failure
- To determine the incidence and consequence of acute kidney injury in patients with SBO
- To determine the incidence and consequence of malnourishment in patients with SBO

Tertiary objectives

- To identify areas of management of patients with SBO requiring optimisation

- To determine the incidence of recurrent SBO at 1-year, 3-year and 5-year follow-up.

3. Methods

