This is a prospective quality assessment study that will be performed across 6 acute general surgical hospitals in Region Øst (Bispebjerg, Herlev, Hillerød, Hvidovre, Køge, Slagelse). Consecutive consenting patients admitted with a diagnosis with SBO will be included from each site over a 3-month period.

Eligible patients will be identified using the following methods during the study period:

- Screening of acute theatre lists
- A data extraction of all diagnoses of ileus (DK567) or subileus (DK566C) from the emergency department and inpatient wards
- A data extraction of from the radiology department of all patients undergoing a small bowel follow-through with water soluble contrast

In the initial study phase, each patient will be followed for 90 days after diagnosis. Relevant clinicopathological variables will be extracted from electronic patient records, which will be entered in a pseudo-anonymised form into a purpose-built REDCap database using a site-specific study number that is individual for each patient. Patient CPR numbers will be stored on secure folders at each site to allow data validation as necessary. The first analysis of the dataset will be performed

once all included patients have reached 90 days follow-up. Patient journals will be accessed again at 1, 3 and 5 years after diagnosis to investigate the tertiary objectives outlined above.

As this study is purely observational, no alterations to standard patient care will be made. The study will be run by a steering committee including senior surgeons acting as local principal investigators from each of the participating centres. An additional collaborator from each centre will be responsible for patient identification and data collection. It is estimated that each centre will identify between 20-30 eligible patients each month, giving a final cohort size of 360-540 patients.

4. Patients

Inclusion criteria

- Age \geq 18 years old
- Radiological or clinical diagnosis of mechanical SBO made from 00:00 on 22/02/2021 until 23:59 on 21/05/2021
- Admitted to one of the 6 participating centres

Exclusion criteria

- SBO presenting within 30 days of a previous abdominal operation

5. Risks and side effects of study

This is a prospective observational study of patient outcomes. As such, there are no risks or potential side effects for the patients that will be included.

6. Access to patient journals

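### The three listed case-finding routes are narrower than the inclusion criterion, and any resulting loss could fall unevenly on patients never operated on

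*Protocol*

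**What the plan says.** Section 3 of the protocol (Methods) sets the sampling rule: "Consecutive consenting patients admitted with a diagnosis with SBO will be included from each site over a 3-month period". Section 4 (Patients) defines eligibility by diagnosis alone: "Radiological or clinical diagnosis of mechanical SBO made from 00:00 on 22/02/2021 until 23:59 on 21/05/2021". It sets no condition on diagnosis code, imaging test or operation.

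Section 3 then lists how eligible patients will be found:

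- The surgical route, which can reach operated patients only: "Screening of acute theatre lists"
- The coding route, which rests on two codes: "A data extraction of all diagnoses of ileus (DK567) or subileus (DK566C) from the emergency department and inpatient wards"
- The imaging route, which rests on one type of study: "A data extraction of from the radiology department of all patients undergoing a small bowel follow-through with water soluble contrast"

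On staffing it adds: "An additional collaborator from each centre will be responsible for patient identification and data collection". It describes no fourth route and no check of completeness.

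Section 1 (Background) says of adhesional SBO in Denmark that "the majority of patients tend to undergo an acute or urgent operation unless there is a clear contraindication to surgery". The primary objective in section 2 is "30-day morbidity and mortality rates of patients admitted with SBO". Two of the secondary objectives concern management itself: the split between operative and non-operative management, and the success rate of non-operative management with its predictors.

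**The concern.** The routes do not span the population that section 4 defines, and they are not equally generous to all patients. An acutely operated patient can be picked up from the theatre list whatever the code and whatever the imaging. A patient not operated on for this episode depends on one of two codes or on one contrast test. Given the Danish practice described in section 1, the acute lists should reach most operated patients, so any shortfall is likelier among those never operated on.

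The two management objectives depend on having both groups in their true proportions. Under-capture of one group is a selection bias. A larger cohort does not reduce it, and an analysis plan cannot recover patients who were never identified.

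**Working it through.** **The plan's own figure.** 6 centres × 3 months × 20 or 30 patients per centre per month = 360 or 540. This agrees with the cohort size in section 3. It is a forecast of patients identified and says nothing about the fraction of eligible patients captured.

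**Routes against the criterion.**

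| Eligible patient | Theatre list | DK567/DK566C | Contrast study |
|---|---|---|---|
| Operated on acutely | reached | if coded so | if done |
| Not operated on acutely, either code | no | reached | if done |
| Not operated on acutely, neither code, contrast study done | no | no | reached |
| Not operated on acutely, neither code, no contrast study | no | no | no |

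The last row meets section 4 and is found by no listed route.

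**Capture model.** All inputs are assumptions, since the protocol gives none of them:

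- p = share starting non-operatively = 0.5
- q = true success among them = 0.6
- f = share of failures who are operated on = 1
- r = capture of never-operated patients divided by capture of operated patients

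Operated = 1 − p + p(1 − q)f = 0.5 + 0.2 = 0.7. Never operated = pq + p(1 − q)(1 − f) = 0.3.

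Observed operative share = operated / (operated + r × never operated). At r = 0.8: 0.7 / (0.7 + 0.24) = 74.5%.

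Observed success = qr / [qr + (1 − q)(f + (1 − f)r)]. At r = 0.8: 0.48 / (0.48 + 0.40) = 54.5%.

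| r | Operative share (true 70%) | Success (true 60%) |
|---|---|---|
| 0.95 | 71.1% (+1.1) | 58.8% (−1.2) |
| 0.9 | 72.2% (+2.2) | 57.4% (−2.6) |
| 0.8 | 74.5% (+4.5) | 54.5% (−5.5) |

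**Dependence on case mix.** With p = 0.3, 0.5, 0.7, q = 0.5 to 0.8 and f = 1:

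| r | Rise in operative share (points) | Fall in success (points) |
|---|---|---|
| 0.95 | 0.6–1.3 | 0.8–1.3 |
| 0.9 | 1.3–2.6 | 1.7–2.6 |
| 0.8 | 2.6–5.5 | 3.8–5.6 |

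**Direction for success.** The formula assumes that never-operated successes and failures are captured equally. Under that assumption, at r = 0.8 and base p and q, success is 57.1% if half of failures are operated on and 60.0% (no bias) if none are. Without it, the sign can reverse:

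- f = 0, successes captured at 90%, failures at 80%: 0.54 / (0.54 + 0.32) = 62.8%.
- f = 0.5, operated patients captured at 100%, successes at 90%, never-operated failures at 60%: 0.54 / [0.54 + 0.4(0.5 + 0.3)] = 62.8%.

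**Scale.** Take operated capture of 90% and never-operated capture of 80%, so r = 0.89. The share is 72.4% and success 57.1%. The 95% half-width, 1.96√(x(1 − x)/n), is 4.6 points (n = 360) or 3.8 points (n = 540) for the share. For success, on 174 or 261 observed non-operative starters, it is 7.4 or 6.0 points.

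**Primary mortality at r = 0.8**, with assumed rates. If 8% of operated and 2% of never-operated patients die, the true rate is 0.7 × 8 + 0.3 × 2 = 6.2% and the observed rate is 0.745 × 8 + 0.255 × 2 = 6.5%. With 5% and 10%, the true rate is 6.5% and the observed rate 6.3%. The shift is 0.3 points or less, in either direction.

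**The case against.** The strongest reply is that nothing shows the missed group to be large. The code extraction takes all diagnoses from both the emergency department and the wards, not just a final or primary diagnosis, so a missed patient must have carried neither code in either setting. Two of the three routes work without an operation, and a collaborator at each centre is responsible for identification. Capture may be near complete. This stands: it limits the size of the problem, but it does not close the gap between the routes and the criterion.

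Several stronger inferences are tempting and are not supported:

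- *The success rate must come out too low.* It need not, as the two 62.8% examples show. Never-operated failures, including deaths, may be captured differently from successes. Differential consent could also act in either direction.
- *Completeness can never be judged unless the route is recorded at the time.* Section 3 keeps CPR numbers at each site for data validation, and section 6 plans further journal access. Route membership might therefore be rebuilt by re-running or linking the extractions.
- *The irreducible herniae named in section 1 show which patients are lost.* Section 1 lists them as an indication for urgent surgery, so most should be on the acute lists. They are no evidence of a shortfall among never-operated patients.

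It may also be said that a sensitivity table belongs in an analysis plan that is not shown. That is fair for the table. The case-finding routes themselves are fixed in section 3 of the protocol.

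**Conclusion.** The point holds as a mismatch inside the protocol that carries a conditional risk of bias. The routes in section 3 cannot reach every patient whom section 4 includes and whom section 3 says will be taken consecutively, and the theatre-list safeguard covers operated patients only. If never-operated patients are captured less often, the operative share is overstated. Success is understated when failures are mostly operated on and never-operated successes and failures are captured equally; otherwise its direction is open.

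A reader might infer that the cohort is materially biased or that the primary result is compromised. The protocol supports neither inference. It gives no capture rates, so every size above rests on assumed values of r, p, q and f. In the base case the effect ranges from about 1 point, which is negligible, to about 5 points at r = 0.8. At r = 0.9 it lies inside the sampling error for either cohort size. The effect on 30-day mortality is small under the assumed rates; morbidity was not worked out. This is a worthwhile and inexpensive improvement to two descriptive secondary objectives.

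**What to change.** 1. In section 3, extend the diagnosis-code extraction beyond DK567 and DK566C to the other codes under which the participating sites record mechanical SBO. The sites should confirm that list, because the protocol does not give it.
2. Add one REDCap field recording which route or routes found each patient, and report the counts by route alongside the operative share and the success rate. Recording this prospectively is the simplest way to gauge completeness.

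Optional: use the overlap of the code and contrast routes to estimate the number missed among never-operated patients, and give a capture-sensitivity range. For illustration, suppose that of 100 such patients codes find 60% and contrast studies 50%, independently. Then 30 are found by both, 30 by code only and 20 by contrast only, and the estimated number missed is 30 × 20 / 30 = 20. If coded patients are also likelier to have a contrast study, this understates the loss.

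The cost is a longer code list in an extraction already planned, one data field, and more false-positive records for the existing site collaborator to review. Patient care does not change.

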Patient journals will be accessed in order to extract relevant clinicopathological data. The local principal investigators are responsible for the relevant study approvals, which should be made as a quality assessment project. As described above, patient journals will be accessed at 4 timepoints during this study:

- Period 1 – from diagnosis until 90 days follow-up
- Period 2 – 1 year after diagnosis
- Period 3 – 3 years after diagnosis
- Period 4 – 5 years after diagnosis

7. Data storage and security

Patient identifiable data will be stored in a secure folder at each specific site. The local principal investigators will be responsible for establishing and maintaining these folders. Only those directly involved with the study will have access to these files. Relevant clinicopathological variables will be entered into a purpose-built REDCap database in an anonymised form. Each site will have a specific REDCap login with site-specific patient study numbers.

Any patient identifiable data will be permanently deleted within 5 years of the study start (i.e. 31/12/2026).

8. Publication of results

This study is registered on www.clinicaltrials.gov – NCT04750811. The results of the study will be published in scientific journals and presented at international conferences.

9. References

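### Could site-specific study numbers and the lack of a first-episode rule put the same patient in the cohort twice?

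*Protocol*

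**What the plan says.** **Entry.** Protocol section 4 requires "Radiological or clinical diagnosis of mechanical SBO made from 00:00 on 22/02/2021 until 23:59 on 21/05/2021" and "Admitted to one of the 6 participating centres". The only exclusion is "SBO presenting within 30 days of a previous abdominal operation". Neither list mentions an earlier SBO episode, an earlier inclusion, or a patient admitted to two of the centres.

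**Case-finding.** Section 3 uses acute theatre lists, contrast follow-through studies and "A data extraction of all diagnoses of ileus (DK567) or subileus (DK566C) from the emergency department and inpatient wards". These are lists of events.

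**Unit.** Section 3 states what is enrolled: "Consecutive consenting patients admitted with a diagnosis with SBO will be included from each site over a 3-month period". Follow-up and the planned size of 360 to 540 are also expressed per patient.

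**Identifiers.** Records enter REDCap "using a site-specific study number that is individual for each patient". Section 7 adds "Each site will have a specific REDCap login with site-specific patient study numbers". On the linking key, section 3 says "Patient CPR numbers will be stored on secure folders at each site to allow data validation as necessary".

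**Outcomes affected.** The primary objective in section 2 is 30-day morbidity and mortality. The proportion managed operatively is a secondary objective, and recurrent SBO at 1, 3 and 5 years is a tertiary one.

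**The concern.** The dated event is a diagnosis, and a person can have more than one within the window. Study numbers are not unique across the study and the key stays at each hospital, so a transferred patient, or one readmitted elsewhere, satisfies the criteria at two sites and receives two numbers.

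Three consequences would follow if this were common:

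- One death or complication could count twice in the primary rates.
- A recurrence, which is itself an outcome, could be entered as a new index case and restart the 30- and 90-day clocks.
- The 30-day post-operative exclusion removes early re-presentations after surgery but none after non-operative care, so repeat entries might lean towards the non-operative group.

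Duplicates would also make confidence intervals slightly too narrow.

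**Working it through.** **1. The plan's own figure.** Section 3 gives 6 centres, 3 months and 20 to 30 patients per centre per month: 6 × 3 × 20 = 360 and 6 × 3 × 30 = 540. The stated range reproduces. It takes the centres' patients as non-overlapping. The window from 22/02/2021 to 21/05/2021 is 89 days inclusive.

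**2. Which duplicate routes the text leaves open.**

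| Route | Text that bears on it | Open? |
|---|---|---|
| Second episode, same centre | Number individual to the patient (section 3); local CPR list | No; a second record would depart from the protocol |
| Transfer between centres | No rule on which centre enters the patient | Yes |
| Readmission to a different centre | No first-episode rule; no cross-site match described | Yes |

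**3. Size, taking the concern at its strongest.** The documents give no rate, so all inputs here are assumptions. Let r be the share of patients entered twice, with true mortality 8% and 20% among those entered twice, every such death being counted on both records.

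Extra records = N × r. Observed mortality = (0.08 + 0.20r)/(1 + r).

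| r | Extra records, N = 360 / 540 | Observed mortality | Shift (points) |
|---|---|---|---|
| 2% | 7.2 / 10.8 | 0.084/1.02 = 8.24% | 0.24 |
| 5% | 18 / 27 | 0.090/1.05 = 8.57% | 0.57 |
| 8% | 28.8 / 43.2 | 0.096/1.08 = 8.89% | 0.89 |

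Sampling error at 8%: 1.96 × √(0.08 × 0.92/360) = 2.8 points, and with 540 it is 2.3 points. Each shift is well inside it.

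**4. Direction.** Now let d be the share of records that are duplicates, and k the risk in those records relative to unique patients. Observed rate = p[(1 − d) + dk]. With p = 10% and d = 5% (assumed), k = 0 gives 9.5%, k = 1 gives 10.0% and k = 3 gives 11.0%. A value of k below 1 is plausible for readmissions, because the patient must survive the first episode to re-enter. A death then counts on both records only if it falls within 30 days of both diagnoses. For a transfer under a single diagnosis the clocks coincide and double counting is complete. The documents do not say which type predominates.

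**5. Precision.** With as many as 10% duplicate records (assumed), 360 records are 324 patients and 540 are 486. For a 10% rate the 95% half-width moves from 3.1 to 3.3 points, or from 2.5 to 2.7.

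**6. Operative against non-operative.** Re-entry after a non-operative first episode need not add a non-operative record, because the patient may be operated on at re-presentation. Section 1 says most adhesional cases in Denmark tend to have surgery. From day 31 after surgery, operated patients can re-enter too. The direction of any distortion is not established.

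**7. Recurrence.** Sections 3 and 6 have journals read to 90 days and again at 1, 3 and 5 years. A re-presentation can still be recorded as a recurrence on the first record even if it also generates a second one. Illustration (assumed): of 100 patients, 10 recur within a year and 5 of these are re-enrolled elsewhere. If all 10 are still counted, incidence is 10/105 = 9.5% against 10%. It falls to 5/105 = 4.8% only if the re-enrolled episodes are left off the first record, and nothing in the protocol directs that.

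**8. Can duplicates be found when it matters?** The last patient reaches 90 days on 19/08/2021 (21/05/2021 plus 90 days). Section 7 puts the end date for deleting identifiers in 2026, so the CPR lists should still exist when the first analysis is prepared.

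**The case for a change.** The strongest opposing case is that the index episode and the enrolling centre belong to eligibility, so an analysis plan cannot supply them afterwards. Every clock runs from a diagnosis that the protocol does not single out. If a second episode became the index, a death 40 days after the first diagnosis could count as a 30-day death. In addition, a database without a shared key cannot reveal its own duplicates, and section 7 even calls its contents anonymised.

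Part of this stands. The protocol writes down no first-episode rule, no rule for the transferred patient and no cross-site match. But the patient is already the stated unit, and the natural reading for a consecutive cohort is that the first qualifying diagnosis in the window starts the clock and later ones are recurrences. The key also survives outside the database. Section 3 describes the entries as pseudo-anonymised and keeps CPR numbers for validation, and the steering committee has a senior surgeon from each centre. Comparing lists is not described, but nothing in the protocol rules it out.

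**Conclusion.** No change to the plan is needed. What remains is a gap in detail: the protocol does not spell out which diagnosis is the index when a patient has several, or who enters a patient admitted to two centres. It affects only cross-centre transfers and readmissions, and analysts can fill it from the patient-level unit and the retained CPR lists. A data-management or analysis plan, which is not to hand, would commonly cover it.

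Under assumed double entry of 2% to 8% and deliberately unfavourable mortality, the primary rate moves by 0.2 to 0.9 points, against sampling error of about 2.3 to 2.8. The documents fix neither the frequency of double entry nor the direction of its effect. A clear lean towards non-operative records, or a substantial loss of recurrences, would require abstraction practices that the protocol does not call for. The conclusion rests on double entry being no more frequent than the assumed range. It also assumes that the centres use the identifiers they keep for the stated purpose of validation.
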